### 8.5 CD14152 Quantification in Biological Sampling

Concentration of nemolizumab in the serum will be determined by the designated CRO using a validated ELISA method.

Results will be

included as an appendix in the final CSR.

Galderma Research & Development, LLC

#### 8.6 Safety Assessments

Safety assessments will be conducted for all subjects at the screening visit (upon signing of the ICF) and at every subsequent visit.

#### 8.6.1 Adverse Events

#### Adverse Event Definition

An AE is defined as any untoward medical occurrence in a clinical study subject administered a medicinal product which does not necessarily have a causal relationship with this treatment. An AE can therefore be any unfavorable and unintended sign (including an abnormal laboratory finding), symptom, or disease temporally associated with the use of a medicinal (investigational) product, whether or not it is related to the medicinal (investigational) product. This includes an exacerbation of pre-existing conditions or events, intercurrent illnesses, drug interaction or the significant worsening of the indication under investigation that is not recorded elsewhere in the case report form (CRF) under specific efficacy assessments.

#### Notes:

[figure not shown]
- Any new sign or symptom reported by the subject that appears after accidental or intentional
  overdose or misuse should be reported as an AE.
- Whenever possible, a diagnosis should be reported on the AE form, instead of signs, symptoms or abnormal laboratory values.
- Pregnancy is not to be considered as an AE; however, it must be monitored and reported as
  described in Section 8.6.1.2.
- Each new episode of a chronic disease (eg, hay fever, allergy, etc) from the screening visit should be reported as a new AE.

CONFIDENTIAL Page 60 of 99

Galderma Research & Development, LLC Protocol Number: RD.06.SPR.116912

21-JUL-2020 Version 6.0

The investigator or designee will report all AEs that occur from the time the ICF is signed until the end of the study. The sponsor/CRO should be informed if the investigator becomes aware of any safety information that appears to be drug related, even after the subject has completed the clinical trial.

Adverse Events assessed as related to the treatment or study procedure will be monitored until they have resolved or reached a stable condition. Other AEs will be monitored until the last visit if they have not resolved or reached a stable condition.

The investigator will obtain and maintain in the subject's files all pertinent medical records, information and medical judgment from colleagues who assisted in the treatment and follow-up of the subject. If necessary, the investigator will contact the subject's personal physician or hospital staff to obtain further details.

## Assessment of Severity

Each AE will be assigned a category by the investigator as follows:

Mild: An AE that is easily tolerated by the subject, causes minimal discomfort and does

not interfere with everyday activities.

Moderate: An AE that is sufficiently discomforting to interfere with normal everyday

activities; intervention may be needed.

Severe: An AE that prevents normal everyday activities; treatment or other intervention

usually needed.

If there is a change in severity of an AE, it must be recorded as a separate event.

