#### **Study Duration:**

Study participation may include a total of 28 weeks for subjects that complete the screening, treatment and follow-up periods. This study includes a 2 to 4-week run-in period followed by a 16-week treatment period. A follow-up visit (Week 24) is scheduled for subjects who will not

CONFIDENTIAL Page 13 of 99

Galderma Research & Development, LLC Protocol Number: RD.06.SPR.116912 21-JUL-2020 Version 6.0

rollover into the nemolizumab long-term extension study. Subjects who prematurely discontinue the study before the Week 16 visit have to be followed for 12 weeks after their last dose of study drug.

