## Documentation and Reporting of Adverse Events

Adverse events should be reported and documented in accordance with the procedures outlined below. All AEs occurring during the study must be documented on the relevant CRF pages. The following data should be documented for each AE:

- · Description of the symptom event
- · Classification of 'serious' or 'not serious'
- Severity
- Date of first occurrence and date of resolution (if applicable)

CONFIDENTIAL Page 62 of 99

- Action taken
- Causal relationship
- Outcome of event (unknown, recovered, not yet recovered, recovered with sequelae, death [with date and cause reported]).

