#### 9.4.3.2 Adverse Events

Treatment-emergent adverse events (TEAEs), defined as those AEs occurring after the first administration of study treatment until the last study visit, will be tabulated in frequency tables by System Organ Class and Preferred Term based on the Medical Dictionary for Regulatory Activities (MedDRA) for each study phase. Additional summary tables will be provided for SAEs, AEs related to the study drug and/or study procedure, AESIs, and AEs leading to treatment discontinuation and study withdrawal. For a given AE, a subject will be counted once even if he/she has experienced multiple episodes of that particular AE.

Pre-treatment AEs will be listed separately.

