10.2. Adverse Events

Adverse events (AEs) will be coded using the Medical Dictionary for Regulatory Activities (MedDRA) Version 21.1. Summaries of AEs will include only treatment emergent AEs (TEAEs) defined as AEs with an onset date/time on or after the date/time of first treatment. AEs with completely missing onset dates/time will be considered as TEAEs. If AE onset date/time is partially missing, the AE will be considered as TEAE unless the non-missing part of date/time proves it started prior to the first treatment date/time.

AEs will be summarized using the number and percent of subjects reporting each system organ class (SOC) and preferred term (PT) and sorted alphabetically by SOC and by descending frequency of PT within SOC. Subjects who experienced multiple events within the same SOC will be counted once in the SOC summary. Subjects who experienced multiple occurrences of events with the same PT will be counted once in the PT summary. Percentages will be calculated using the total number of subjects in the Safety population.

The following summary tables for AEs will be presented:

- Overall Summary of Treatment Emergent Adverse Events (TEAEs), All Causalities
- Overall Summary of Treatment Emergent Adverse Events (TEAEs), Study Drug Related
- Treatment-Emergent Adverse Events (TEAEs) by System Organ Class and Preferred Term, All Causalities
- Treatment Emergent Adverse Events (TEAEs) by System Organ Class and Preferred Term,
 Study Drug Related
- Serious Treatment-Emergent Adverse Events (TEAEs) by System Organ Class and Preferred Term, All Causalities
- Serious Treatment Emergent Adverse Events (TEAEs) by System Organ Class and Preferred Term, Study Drug Related

- Treatment-Emergent Adverse Events (TEAEs) by System Organ Class, Preferred Term, and Maximum Severity, All Causalities
- Severe Treatment Emergent Adverse Events (TEAEs) by System Organ Class and Preferred Term, All Causalities
- Severe Treatment Emergent Adverse Events (TEAEs) by System Organ Class and Preferred Term, Study Drug Related
- Treatment-Emergent Adverse Events (TEAEs) Leading to Permanent Discontinuation of Study Drug by System Organ Class and Preferred Term, All Causalities
- Treatment Emergent Adverse Events (TEAEs) Leading to Permanent Discontinuation of Study Drug by System Organ Class and Preferred Term, Study Drug Related
- Treatment-Emergent Adverse Events (TEAEs) of Special Interest by System Organ Class and Preferred Term, All Causalities

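### Every AE severity change becomes a separate record while TEAEs are defined by onset timing alone, so a run-in AE that changes grade after first dose can be misclassified

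*Protocol*

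**What the plan says.** **Collection.** Protocol 8.6.1 (Notes) has AEs reported from consent: "The investigator or designee will report all AEs that occur from the time the ICF is signed until the end of the study". The Synopsis states: "This study includes a 2 to 4-week run-in period followed by a 16-week treatment period". AE records will therefore exist before first dose.

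**Severity.** Each AE is graded mild, moderate or severe. Protocol 8.6.1 (Assessment of Severity) then adds: "If there is a change in severity of an AE, it must be recorded as a separate event". The sentence is not limited to worsening.

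**Dates.** For each AE, Protocol 8.6.1 (Documentation and Reporting) asks for "Date of first occurrence and date of resolution (if applicable". It does not say which start date a severity-change record takes.

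**Treatment emergence.** In SAP 10.2, TEAEs are "defined as AEs with an onset date/time on or after the date/time of first treatment". Protocol 9.4.3.2 has them "defined as those AEs occurring after the first administration of study treatment until the last study visit". Neither sets a condition on severity relative to the pre-dose period.

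**Counting.** SAP 10.2 also states: "Subjects who experienced multiple occurrences of events with the same PT will be counted once in the PT summary". In the maximum-severity table, the worst occurrence is used.

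**The concern.** The recording rule splits one illness into several records, and the analysis rule then treats each record as an event of its own. An illness that began in the run-in and is getting better can appear as something that emerged on treatment.

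TEAE incidence is a primary safety endpoint (Protocol 6.2.3). It also feeds the interim assessment of whether adolescent safety resembles adult safety, on which recruitment of adolescents into Phase 3 rests (Protocol 7.1, SAP section 13). There is one treatment group, so no concurrent control would carry the same artefact. With about 20 subjects, and about 10 at the interim, one subject visibly moves a percentage. SAP 10.2 also plans two tables of terms seen in more than one subject, and one spurious record plus one true one would place a term in both.

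Elsewhere the plan does separate pre-existing from emergent findings. Under Protocol 8.6.2, a clinically significant laboratory value after screening is an AE only if it is new or worse since screening. The potentially clinically significant laboratory limits in SAP section 21 are conditioned on the baseline value. The TEAE definition has no equivalent.

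**Working it through.** The plan states no figure on this point. The check applies its rules to example records and then sizes the effect.

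**Inputs**
- Recording rule and severity grades: Protocol 8.6.1.
- TEAE rule: SAP 10.2 and Protocol 9.4.3.2.
- N = 20 (final) and N = 10 (interim), both approximate: Protocol 7.1.
- q, the share of subjects with a run-in AE that falls a grade after first dose without resolving: not in the documents. Assumed 2% to 10%.

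**Step 1: example records.** Reading A dates the new record at the severity change. Reading B carries the original start date forward. The target column counts an event only if it is new or more severe than before dosing.

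| Event | Before first dose | After first dose | Target | Reading A | Reading B |
|---|---|---|---|---|---|
| Headache | moderate, from Day -8 | mild, from Day 5 | not a TEAE | TEAE | pre-treatment |
| Nausea | mild, from Day -8 | moderate, from Day 5 | TEAE | TEAE | pre-treatment |
| Cough | none | mild, from Day 12 | TEAE | TEAE | TEAE |
| TEAEs counted | | | 2 | 3 | 1 |

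Reading A adds the improving headache. Reading B drops the worsening nausea. Neither gives the target.

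**Step 2: does another rule correct this?** Counting once per preferred term and taking the worst severity both operate among records already classed as TEAEs. Neither looks back at a pre-dose record, and neither document links a severity-change record to its parent event.

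**Step 3: weight of one subject (Reading A).** 100/20 = 5 percentage points at the final analysis; 100/10 = 10 points at the interim. This holds only if the subject has no other TEAE in that term, since each subject counts once.

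**Step 4: chance that at least one subject is affected (Reading A).** With independent subjects, P = 1 - (1 - q)^N.

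| q (assumed) | N = 20 | N = 10 |
|---|---|---|
| 2% | 1 - 0.98^20 = 33% | 1 - 0.98^10 = 18% |
| 5% | 1 - 0.95^20 = 64% | 1 - 0.95^10 = 40% |
| 10% | 1 - 0.90^20 = 88% | 1 - 0.90^10 = 65% |

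A run-in AE that is mild at first dose cannot contribute, because it can only resolve, stay the same or worsen.

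**The case against.** **The onset date is inferred.** The protocol does not say that a severity-change record starts on the day of the change. The field asks for first occurrence, which a site could take as the start of the illness, and CRF completion instructions are not among the documents. This stands, and it is why the point is conditional. It does not rescue the rule, because carrying the date forward hides post-dose worsening.

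**A change might mean worsening only.** An AE is an untoward occurrence, and an improvement fits that poorly. But the severity sentence says change without qualification, and a site following it literally would open a record for a decrease.

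**The size is soft.** The event must be moderate or severe at dosing and step down rather than resolve. At q = 2% the chance that nobody is affected is 67% at N=20 and 82% at the interim. A reader might infer a definite number of false TEAEs; the documents give no rate to support one.

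**Over-counting is cautious and can be seen.** The SAP already counts completely missing onset dates as treatment-emergent. The interim outputs include both the TEAE listing (16.2.7.1) and the pre-treatment AE listing (16.2.7.2), so with about 10 subjects a paired record can be spotted. This tempers the consequence. It does not correct the summary tables, and Reading B errs in the incautious direction.

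**Drug-related tables.** A reader might infer that these records drift into the related tables because SAP 10.2 treats missing relatedness as related. That needs a further data failure, since Protocol 8.6.1 asks for causality on every AE. It does not follow from the severity rule.

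**Conclusion.** The point holds in conditional form. The recording rule and the timing-only TEAE definition, taken together, misclassify some run-in events under either reading of the onset date. Under the likelier reading, an event that improves by a grade after first dose without resolving is counted as a TEAE. Under the other, a true worsening is left out.

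For the likelier reading, the size is 5 points per affected subject at N=20 and 10 at N=10, within a term where that subject has no other TEAE. The chance of at least one affected subject is 33% to 88% and 18% to 65% respectively, resting on an assumed share of 2% to 10% and independent subjects.

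A reader might go further and infer that the interim comparison with adults is biased. The documents do not support that: they set no numerical TEAE criterion for similarity and do not show the TEAE definition used in the adult studies. If that definition was the same, the artefact may be common to both sides. The correction is still worth making, because a stated rule gives a wrong count on a primary safety endpoint and is cheap to repair.

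**What to change.** In SAP 10.2, define a TEAE as either an event whose first start is at or after first dose, or a pre-treatment event whose severity after first dose exceeds its worst pre-treatment severity. Link each severity-change record to its parent event by a CRF field or, failing that, by preferred term with contiguous end and start dates. State that continuation records of equal or lower severity are not TEAEs. State also which start date a severity-change record carries, so that the derivation does not depend on site habit.

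Protocol 9.4.3.2 has no worsening condition and SAP section 14 foresees no change from the protocol, so record the revised definition there as a departure.

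Cost: a short definition, a small derivation step and some data review to link records. If linkage uses preferred term and dates, data collection need not change. Before adopting it, check the definition used for the adult comparison data; if it differs, present the TEAE tables both ways so that the comparison is like with like.

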### Assessment of Causality

The investigator is to determine whether there is a reasonable causal relationship between the
occurrence of the AE and exposure to the study drug (ie, nemolizumab) and/or study procedure
(eg, injection, TCS, blood sample collection).

CONFIDENTIAL Page 61 of 99

The relationship assessment for an AE is to be completed using the following definitions as a guideline for all AEs occurring during this clinical trial.

## Reasonable Possibility:

According to the reporting investigator, there is a reasonable possibility (ie, suggestive evidence or arguments) that there is a causal relationship irrespective of the dose administered:

- Between the study drug (nemolizumab) and the AE, and/or
- Between the clinical trial protocol procedure (eg, injection, TCS, blood sample collection) and the AE

#### No Reasonable Possibility:

No suggestive evidence or arguments can be identified regarding a causal relationship between the study drug or the clinical trial protocol procedure and the AE.

#### Action Taken

The investigator will describe the action taken in the appropriate section of the CRF, as follows:

- None
- Study drug stopped
- Study drug temporarily interrupted
- · Concomitant medication
- Other, specify.

#### Follow-up of Adverse Events

All investigators should follow up subjects with AEs until the event is resolved or until, in the opinion of the investigator, the event is stabilized or determined to be chronic. Details of AE resolution must be documented in the CRF.

Subjects should be followed up for 12 weeks (±5 days) after receiving the last dose of study drug, and any AEs that occur during this time should be reported according to the procedures outlined above.

## Documentation and Reporting of Adverse Events

Adverse events should be reported and documented in accordance with the procedures outlined below. All AEs occurring during the study must be documented on the relevant CRF pages. The following data should be documented for each AE:

- · Description of the symptom event
- · Classification of 'serious' or 'not serious'
- Severity
- Date of first occurrence and date of resolution (if applicable)

CONFIDENTIAL Page 62 of 99

- Action taken
- Causal relationship
- Outcome of event (unknown, recovered, not yet recovered, recovered with sequelae, death [with date and cause reported]).

#### 8.6.1.1 Adverse Events of Special Interest

An AESI is a noteworthy event for the study drug that should be monitored closely and reported immediately. See Section 8.6.1.4 for reporting procedure. An AESI can be either serious or non-serious.

Based on the potential risks of nemolizumab and the risks associated with biologics (and their biosimilar equivalents) in general (ie, class effects), the following AEs will be considered AESIs:

- Injection-related reactions
  - Anaphylactic reactions
  - Acute allergic reactions requiring treatment
  - Severe ISR (ie, lasting > 24 hours)
- Newly-diagnosed asthma or worsening of asthma
  - More specifically, subjects with a medical history of asthma must be referred to the physician who manages their asthma when:
    - ACT score ≤ 19; an ACT score ≤ 19 conveys asthma which may not be adequately controlled. An AESI is reported based on the investigator's clinical judgment of the managing physician's report.
    - PEF < 80% of the predicted value; an AESI should be reported.

    - Unexpected worsening of asthma is observed or reported. An AESI is reported based on the investigator's clinical judgment.
  - Subjects without a medical history of asthma must be referred to an appropriate respiratory physician/specialist when:
    - Signs and/or symptoms suggestive of asthma have been observed or reported. An AESI is reported based on the investigator's clinical judgment of the specialist's report.
    - Respiratory assessment suggests a decline in the subject's respiratory health. An AESI is reported based on the investigator's clinical judgment of the specialist's report.
- Infections
  - Any severe infection, or any infection requiring treatment with parenteral antibiotics, or oral antibiotics/antivirals/antifungals for > 2 weeks
- Peripheral edema: limbs, bilateral
- Facial edema

CONFIDENTIAL Page 63 of 99

Elevated ALT or AST (> 3 × ULN) in combination with elevated bilirubin (> 2 × ULN)

#### 8.6.1.2 Serious Adverse Events

An SAE is any untoward medical occurrence or effect that, at any dose,

- Results in death.
- Is life-threatening (an AE is life-threatening if the subject was at immediate risk of death from the event as it occurred, ie, it does not include a reaction that might have caused death if it had occurred in a more serious form).
- Requires or prolongs inpatient hospitalization. (Complications occurring during
  hospitalization are AEs and SAEs if they cause prolongation of the current hospitalization.
  Inpatient hospitalization is considered to have occurred if the subject has had to stay for a
  night at the hospital. The criterion for prolongation of hospitalization is also defined as an
  extra night at the hospital. Hospitalization may not constitute sufficient grounds to be
  considered as an SAE if it is solely for the purpose of diagnostic tests [even if related to an
  AE], elective hospitalization for an intervention that was already planned before subject
  enrollment in the clinical trial, admission to a day-care facility, social admission [eg, if the
  subject has no place to sleep], or administrative admission [eg, for a yearly examination].
  The details of such hospitalizations must be recorded on the medical history or physical
  examination CRF).
- Results in persistent or significant disability/incapacity. (An AE is incapacitating or disabling if it results in a substantial and/or permanent disruption of the subject's ability to carry out normal life functions).
- Results in a congenital anomaly/birth defect.
- An important medical event that may not result in death, be life-threatening, or require
  hospitalization, may be considered an SAE when, based upon appropriate medical judgment,
  the event may jeopardize the safety of the subject, and may require medical or surgical
  intervention to prevent one of the outcomes listed above in this definition. Examples of such
  events are intensive treatment in an emergency room or at home for allergic bronchospasm,
  blood dyscrasia, or convulsions that do not result in hospitalization.

#### 8.6.1.3 Procedure for Reporting a Serious Adverse Event

For any SAE occurring during the clinical trial, regardless of whether or not related to the study drug and/or procedure, the investigator must:

- Take prompt and appropriate medical action, if necessary. The safety of the subject is the first priority.
- Ensure that the event is evaluated as an SAE. Immediately notify (within 24 hours of receipt of the event) the CCI Safety and Pharmacovigilance group of an SAE report, by email or fax:

Fax No.: PPD

Safety email: PPD

CONFIDENTIAL Page 64 of 99

Note: Immediate SAE reporting is required by the investigator if it occurs during the clinical study or within 12 weeks (± 5 days) of receiving the last dose of study drug, whether or not the event is considered to be related to the investigational product.

The demographics, medical history, drugs/therapies, and medical and surgical procedures forms must also be available for review in CRF, at that time.

- Send any relevant information or anonymized medical records (eg, laboratory test results) to the College Safety and Pharmacovigilance group (see contact details above), within 24 hours of receipt of this relevant information.
- Monitor and record the progress of the event until it resolves or reaches a stable condition, with or without sequelae. For all additional follow-up evaluations, complete an updated SAE form within 24 hours of receipt of the updated information.
- Obtain and maintain in the subject files all pertinent medical records, information, and
  medical judgments from colleagues who participate in the treatment and follow-up of the
  subject. If necessary, contact the subject's personal physician or hospital staff to obtain
  further details.
- When the outcome of the event is known, complete an updated SAE form, if appropriate.
- 7. Prompt notification of SAEs by the investigator is essential so that legal obligations and ethical responsibilities toward the safety of subjects are met. The sponsor has a legal responsibility to notify both the local regulatory authority and other regulatory agencies about the safety of a product under clinical investigation. The sponsor or its delegate (ie, the CRO) will comply with country-specific regulatory requirements relating to safety reporting to regulatory authorities, Institutional Review Board (IRB)/Independent Ethics Committee (IEC) and investigators. Investigator safety reports are prepared for Suspected Unexpected Serious Adverse Reactions (SUSARs) according to local regulatory requirements, and are forwarded to investigators as necessary.

An investigator who receives an investigator safety report describing an SAE(s) or other specific safety information (eg, summary or listing of SAEs) from the sponsor or its delegate (ie, the CRO) will file it with the IB and will notify the IRB/IEC, if appropriate according to local requirements.

 Comply with the applicable regulatory requirement(s) related to the reporting of SAEs to the IRB/IEC.

